5.2.2. Inclusion / Exclusion Criteria

Inclusion Criteria

Patients are required to:

- 1. Have CPRD-GOLD data of acceptable research quality according to CPRD standards.
- 2. Be new users of LABD or ICS-containing medications from January 2002-December 2010
- 3. Have a COPD diagnosis at any time in the period prior to and including the Cohort Entry Date (to eliminate any patients with asthma only)
- 4. Have at least one year of data prior to Cohort Entry Date.
- 5. Be at least 45 years of age at Cohort Entry Date.
- 6. Have GPRD-HES linkage. (Note: these individuals need to be retained for basic demographics but are not part of the new user cohort).
- 7. Have HES coverage one year prior to the Cohort Entry Date

Exclusion Criteria

1. Patients with an occurrence of a code for a medical condition incompatible with COPD diagnosis any time in their history. This list contains conditions that are a related to lung or bronchial developmental anomalies, degenerative processes (cystic fibrosis, pulmonary fibrosis), bronchiectasis, pulmonary resection or other significant respiratory disorders other than COPD (but not including cancer) that can interfere with clinical COPD diagnosis or substantially change the natural history of the disease.

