5. METHODOLOGY

5.1. Feasibility Assessment

Prior to conducting this study, two feasibility assessments were conducted to support the study objectives including a preliminary feasibility assessment and more refined assessment following cohort selection. The feasibility informs on the number of patients in each pre-defined group of new users of respiratory medications and the number of patients meeting different definitions of pneumonia. These figures will allow for an assessment of the available statistical precision to examine treatment group differences.

Mannino and colleagues found a rate of pneumonia requiring hospitalization to be 22.7 per 1,000 person years among patients with advanced disease (GOLD stage airflow limitation III or IV) [Mannino, 2009]. A previous study of community-acquired pneumonia (CAP) in a primary care population of patients with COPD in the GPRD [Müllerova, 2012], there were approximately 40,000 patients with prevalent COPD in CPRD-GOLD between 1996-2006 with ~8% experiencing pneumonia (CAP without restricting to those requiring hospitalization) during the study period with a CAP rate of 22.4 per 1000 person years. The authors included a highly sensitive definition of pneumonia, resulting in 1,469 cases of CAP in their case-control study.

Feasibility results on the 2005-2010 study period included approximately 12,000 new users and 185 pneumonia events. When expanding to include the study period 2002-2010, there will be approximately 18,742 new users of ICS-containing medications (n=12,065) or long-acting bronchodilators (LABD) based on requiring CPRD-GOLD linkage to HES, and hospitalization data 12-mo prior to the new user prescription as presented in Table 1. These totals include the application of all inclusion/exclusion criteria; however, additional subjects may get excluded in the final analysis based on censoring and on-going pneumonia at the time of cohort entry.

Number		F	1	Year o	f Cohort	Entry	F			
of New	0000	0000	0004	0005	0000	0007	0000	0000	0040	T - 4 - 1
Users	2002	2003	2004	2005	2006	2007	2008	2009	2010	lotal
LABD	354	513	703	765	715	723	972	938	994	6,677
ICS-										
containing ^a	1,828	1,499	1,633	1,369	1,310	1,207	1,244	1,100	875	12,065
Total by										
Year	2,182	2,012	2,336	2,134	2,025	1,930	2,216	2,038	1,869	18,742

Table 1 Feasibility Results: New User Cohort

 ICS-Containing=inhaled corticosteroid-containing medications, LABA=long-acting beta-agonists, LAMA=longacting antimuscarinics

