5.2. Study Design

This will be a retrospective cohort design.

CPRD-GOLD data will be used to identify a 'new-user' COPD cohort to evaluate a relationship between an exposure to respiratory medications, long-acting bronchodilators (LABD) or ICS-containing medications and the first episode of the pneumonia types of interest.

New users of ICS-containing medications or long-acting bronchodilator (LABD) would be evaluated in a cohort design for the occurrence of pneumonia following their designation as new users. Specific medications are described in Section 5.2.1. To adjust for anticipated differences in confounding by severity between the two treatment groups, important patient characteristics relating to COPD severity and pneumonia would be evaluated in the patient history in the period prior to and including the new user date. Propensity scores (PS) would be generated using these characteristics. The study schematic is presented in Figure 1.

Figure 1 Study Schematic: New User Cohort Design 2002-2010

A strength of the new-user design is that patient follow-up starts with the initial medication prescription written by the healthcare provider for all treatment groups and avoids potential biases that result from examining prevalent users relating to survivor bias and changes in their covariates based on exposure to treatment [Ray, 2003].

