5.2.1. New User Study Population

Based on the treatment guidelines, we expect the potential for differences in COPD severity between treatment groups that require adjustment in the analysis. For the treatment of COPD, there is a consensus document on the treatment paradigm for patients with COPD [GOLD, 2009]. A LABD is recommended as an initial maintenance treatment in patients with COPD, including long-acting antimuscarinics (LAMA) or long-acting beta-agonists (LABA). If the disease severity warrants, adding additional therapy (a second bronchodilator or ICS) is recommended. However, an internal unpublished analysis estimated that ~10% of patients at COPD diagnosis are prescribed triple therapy (LABA, LAMA, ICS) during the period 2008 -2009.

CPRD-GOLD data are available through December 22, 2011 with the 1Q2011 data load. HES data are available through August 2011 with the latest data load. Therefore, patients are examined to identify new users between January 2002 and December 31, 2010 to allow for time in the cohort after being identified as a new user and prior to censoring of available data. If the data availability changes, the study period will adjust accordingly in the analysis plan.

The **Baseline Period** is the one-year period prior to Cohort Entry Period to confirm new user status and evaluate patient characteristics of interest.

Identifying New Users

For the purposes of this study, a new user will be defined as someone who has not used medications of interest (ICS-containing or LABD containing medications) in the year prior to a new prescription of a medication of interest (ICS-containing of LABD). The one-year period of no use is referred to a washout period rather than requiring no use of these medications ever in the patient's history. New users of ICS-containing medications and new users of LABD would be identified separately, and are described in Figure 2.

The following patients would not be considered new users:

- New users of triple therapy (LABA/LAMA/ICS) in three single inhalers or ICS/LABA inhaler plus LAMA
- Patients who step up from LABD to ICS/LABA combination therapy in a single device (based on definition of a new user, they have LABD in the history)

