5.3. Data

This study will use the Clinical Practice Research Datalink's (CRPD)-GP OnLine Database (GOLD), a primary care research database in the United Kingdom. We will also include the following data with linkages to CPRD-GOLD:

- Hospital Episode Statistics through August, 2011 (http://www.hesonline.nhs.uk/Ease/servlet/ContentServer?siteID=1937&categoryID =289)
- Office of National Statistics Mortality File or CPRD mortality information through March, 2011 (http://www.ons.gov.uk/ons/rel/subnational-health1/the-21st-century-mortality-files/2010/index.html) [Note: If we do not get access to ONS, we would use CPRD-GOLD algorithms for death in addition to the HES discharge status.]
- Townsend Deprivation Scores (http://www.communities.gov.uk/documents/communities/pdf/733520.pdf)

CPRD-GOLD data were formally referred to as the General Practice Research Database (GPRD). To prevent confusion between the database and the Global Initiative for Chronic Obstructive Lung Disease (GOLD), which characterizes COPD severity and treatment guidelines, the protocol refers to the database as CPRD-GOLD. CPRD-GOLD contains computerized health care information entered by General Practitioners in the United Kingdom (UK). More than 600 General Practices have been contributing medical history data since 1987, with more than 6 million patients in the database. The database contains longitudinal data recorded by the GP on patient demographic and clinical characteristics, medical history including records of referrals to consultants and hospitalizations, primary care utilization, and prescription medication history over a period of up to 15 years. Descriptive and pharmacoepidemiological studies of patients with COPD have been conducted in CPRD-GOLD, including validation of physicianrecorded COPD diagnosis [Soriano, 2001] and evaluation of COPD co-morbidities [Soriano, 2005]. Studies of pneumonia have also been conducted, including a study of CAP in CPRD-GOLD [Müllerova, 2012] and a validation study of CAP requiring hospitalization in The Health Improvement Network (THIN), which uses the same software as CPRD to capture primary care information [Meropol, 2012].

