5.6. Confounders

Key risk factors for pneumonia that may also relate to treatment will be measured in the one-year Baseline Period. For the purposes of general co-morbidity assessment and vaccination for pneumonia, a longer history will be examined. Although patients may have varying periods of history, this is not expected to be differentially recorded by treatment (which could result in information bias). A longer look back period is needed to identify co-morbidities given they may not be recorded in the Baseline Period.

Confounders that are based on "counts" of healthcare encounters and exacerbation will be categorized during analysis (e.g., tabular summaries, propensity score creation, Cox modeling).

Variable	Parameterization
Age at Cohort Entry	Age will be treated either as a continuous variable, or as a categorical one (see Table shells for intervals)
Gender	Male=1 or Female=0
Body Mass Index (BMI) during Ever in Patient History	Weight in kilograms divided by height in meters squared, will be utilised as a categorical variable using the following categories widely referenced as WHO classification: Underweight (Below 18.5), Normal (18.5 - 24.9), Overweight (25.0 - 29.9), and Obese (30.0 and greater).
	For modelling, the following cutoff values will also be examined: BMI<21, BMI 21-24.9, BMI ≥25.
Smoking status during Ever in Patient History	Four categories will be created: ex-smoker, current smoker, non-smoker, and unknown smoking status containing patients with missing entries or other types of tobacco exposure (e.g. passive smoking). Non-smoker will be the referent group in modelling.
Overall Social Deprivation Scores for England	The deprivation quintile is derived the 32,482 areas of social deprivation, with 1 being most deprived and 32,482 being least deprived. quintiles will be identified as follows (with least deprived the referent in modelling). Quintiles are provided by CPRD:

Variable	Parameterization
Townsend Scores	Quintile. Townsend scores will be described by quintile, as provided by CPRD-GOLD.
Charlson Co-morbidity index and individual chapters Ever in Patient History (prior to Cohort Entry Date)	Charlson's comorbidity index chapter indicator measures will be created using a recently published algorithm by Khan and colleagues [Khan, 2010] after removing COPD and AIDS from the disease list. Some patients may have COPD and some may not (incident diagnosis). AIDS will be excluded due to very low prevalence in the general population.

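### Exclusion criterion 1 has no cut-off at Cohort Entry, so read literally it lets diagnoses first coded after entry decide who is in the cohort

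*Protocol*

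**What the plan says.** Section 5.2.2 has a single exclusion criterion: "Patients with an occurrence of a code for a medical condition incompatible with COPD diagnosis any time in their history". It covers developmental anomalies, fibrosis, bronchiectasis, pulmonary resection and other significant respiratory disorders. No date closes the window.

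Other rules on history do state a limit:
- Inclusion criterion 3, in the same section: "Have a COPD diagnosis at any time in the period prior to and including the Cohort Entry Date".
- The Charlson row of Section 5.6: "Ever in Patient History (prior to Cohort Entry Date". The additional co-morbidities row carries the same restriction.

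The record available to a program runs well past entry. Section 5.3 lists "Hospital Episode Statistics through August, 2011", and Section 5.2.1 puts the end of CPRD-GOLD data at 22 December 2011, while entry runs from 2002 to 2010.

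The criterion is used twice: for the New User Cohort, and again in Section 5.7.3 for new users without HES linkage. Section 5.1 says the Table 1 counts already reflect all eligibility criteria.

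**The concern.** A new-user cohort should be formed from what is known at time zero. Section 5.2 presents the start of follow-up at the first prescription as a strength of the design. If a code at any point in the extract can exclude, a 2003 entrant whose bronchiectasis is first coded in 2008 leaves the cohort, and a pneumonia in 2004 leaves too. Remaining in the study then depends on what happens after entry.

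The excluded conditions are lung diseases, so their later recording may be related to the outcome. One possible route is imaging after a chest infection; the protocol neither states nor rules this out. If there is such a link, incidence rates, risk-factor estimates and the treatment estimate can all be affected. Patients removed at the eligibility step are not available to be weighted back in.

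This is not a detail for the analysis plan. Eligibility is fixed in the protocol, and two programs that both comply with the text could produce different cohorts.

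**Working it through.** **1. What the wording allows.** Inclusion criterion 3 and the two co-morbidity rows add an explicit limit; exclusion criterion 1 does not. Yet the protocol also uses history for the record before entry. Section 5.2 says characteristics "would be evaluated in the patient history in the period prior to and including the new user date", and Section 5.2.1 says of patients stepping up that "they have LABD in the history". The BMI and smoking rows of Section 5.6 say ever in history with no limit and are clearly baseline measures. On the other hand, GOLD stage and MRC dyspnea may use data up to 3 months after entry, so pre-entry is not a uniform default. Post-entry exclusion is therefore a permitted reading, not a stated procedure.

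**2. Reproducing Table 1 (Section 5.1).**
- LABD row: "354 513 703 765 715 723 972 938 994 6,677". The nine years sum to 6,677.
- ICS-containing row: "1,828 1,499 1,633 1,369 1,310 1,207 1,244 1,100 875 12,065". The nine years sum to 12,065.
- Total: 6,677 + 12,065 = 18,742, as stated.
- Entry in 2002–2004: ICS 4,960/12,065 = 41.1%; LABD 1,570/6,677 = 23.5%.

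**3. Potential later record.** Assumptions: mid-year entry, record to 31 August 2011, no death or transfer. The end of record is 9.667 years after 1 January 2002; less 0.5 for mid-year entry, this is 9.167.
- Mean entry offset from 2002, Σn(year − 2002)/Σn: ICS 42,311/12,065 = 3.507; LABD 31,039/6,677 = 4.649.
- Later record: ICS 9.167 − 3.507 = 5.66 years; LABD 9.167 − 4.649 = 4.52 years.
- Ratio: 5.660/4.518 = 1.25.

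Sensitivity of the ICS excess:

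| Assumption | To Aug 2011 | To 22 Dec 2011 |
|---|---|---|
| No loss, mid-year entry | 25% | 24% |
| No loss, entry at start or end of year | 23% or 28% | 21% or 26% |
| 5% loss per year, both arms | 22% | 21% |
| 10% loss per year | 20% | 18% |
| 20% loss per year | 16% | 14% |

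**4. Where the excess comes from.** Within one entry year, both arms have the same potential record. Giving both arms the pooled entry-year mix gives (12,065 × 5.660 + 6,677 × 4.518)/18,742 = 5.25 years in each, a ratio of 1.00. Year of cohort entry is a Section 5.6 covariate, and Section 5.7.4 enters all Section 5.5 and 5.6 variables in the propensity score used for weighting. The incidence rates and rate ratio of Section 5.7.2 are described without weighting.

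**5. Illustration only.** The protocol gives no rate h of post-entry codes. Averaging 1 − exp(−hT) over entry years, to August 2011 without loss:

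| Assumed h per year | ICS removed | LABD removed |
|---|---|---|
| 0.5% | 2.8% | 2.2% |
| 1% | 5.5% | 4.4% |
| 2% | 10.6% | 8.5% |

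Suppose those removed had three times the pneumonia risk of those kept (assumption). The full-cohort rate is then (1 + 2f) times the retained rate, where f is the fraction removed. At h = 1% per year the factors are 1.109 for ICS and 1.088 for LABD. Retained crude rates would be about 10% and 8% too low, and the crude ratio would move by 1.109/1.088 = 1.02. At h = 0.5% and 2% the ratio moves by about 1.01 and 1.035. With equal risk there is no shift; with lower risk the sign reverses.

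**The case against.** The strongest reply is that history already means the record before entry. Sections 5.2 and 5.2.1 use it so, the BMI and smoking rows omit a limit without anyone supposing they use later data, and nothing in the protocol says later codes decide eligibility. This stands in part: it makes the text ambiguous, and the sponsor may have intended the pre-entry reading. It does not settle the matter, because the authors wrote the limit out elsewhere and the criterion's purpose, protecting the COPD diagnosis, would also fit a search of the full record.

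A reader might infer from the 25% that the ICS arm loses more patients and that weighting cannot correct this, so that the hazard ratio is biased between arms. The documents do not support that. The excess is an entry-year effect, and entry year is in the propensity score. What weighting does not address is selection related to the outcome within an entry year, or a rate of later codes that differs by treatment. The protocol gives no information on either.

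A reader might also set the number of patients removed against the 107 severe events (106 severe CAP and 1 HAP) in Table 4. Patients and events are not comparable: at the cohort average of 107/18,742 = 0.57%, 100 removed patients would carry about 0.6 severe events.

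Finally, time at risk is short. Section 5.7.8 implies 283/0.0158 ≈ 17,900 to 106/0.0053 = 20,000 person-years, about 1 year per patient. Most of the 4.5 to 5.7 years of later record therefore falls after censoring, which weakens the link between late codes and analysed events. It does not remove the problem: a late code would still delete the patient and any earlier event.

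**Conclusion.** The point holds as a gap in the eligibility wording. Exclusion criterion 1 lacks the cut-off given to comparable rules and, read literally, conditions the cohort on information from after entry. That can bias incidence rates, risk-factor estimates and the treatment estimate. Size and direction cannot be computed, because the protocol reports neither a rate of post-entry codes nor the pneumonia risk of those who would be removed; the percentages removed rest on assumed rates. The 25% longer record for ICS users is an administrative maximum, about 14% to 22% with 5% to 20% yearly loss. It bears on crude rates and should not be presented as a differential bias in the weighted hazard ratio. Table 1 is already net of exclusions, so the entry-year mix before exclusion may differ slightly.

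**What to change.** Reword exclusion criterion 1 to a code for an incompatible condition at any time up to and including the Cohort Entry Date. Ignore later codes when forming both the New User Cohort and the group of new users without HES linkage. Check which window the feasibility program used; if it searched the full record, re-run Tables 1 and 4 and carry any change into Section 5.7.8.

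The cost is one phrase in Section 5.2.2, one date condition in the cohort program and possibly a re-run of the counts. The downside is that a few patients whose alternative diagnosis is recognised only later stay in the cohort.

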5.3. Data

This study will use the Clinical Practice Research Datalink's (CRPD)-GP OnLine Database (GOLD), a primary care research database in the United Kingdom. We will also include the following data with linkages to CPRD-GOLD:

- Hospital Episode Statistics through August, 2011 (http://www.hesonline.nhs.uk/Ease/servlet/ContentServer?siteID=1937&categoryID =289)
- Office of National Statistics Mortality File or CPRD mortality information through March, 2011 (http://www.ons.gov.uk/ons/rel/subnational-health1/the-21st-century-mortality-files/2010/index.html) [Note: If we do not get access to ONS, we would use CPRD-GOLD algorithms for death in addition to the HES discharge status.]
- Townsend Deprivation Scores (http://www.communities.gov.uk/documents/communities/pdf/733520.pdf)

CPRD-GOLD data were formally referred to as the General Practice Research Database (GPRD). To prevent confusion between the database and the Global Initiative for Chronic Obstructive Lung Disease (GOLD), which characterizes COPD severity and treatment guidelines, the protocol refers to the database as CPRD-GOLD. CPRD-GOLD contains computerized health care information entered by General Practitioners in the United Kingdom (UK). More than 600 General Practices have been contributing medical history data since 1987, with more than 6 million patients in the database. The database contains longitudinal data recorded by the GP on patient demographic and clinical characteristics, medical history including records of referrals to consultants and hospitalizations, primary care utilization, and prescription medication history over a period of up to 15 years. Descriptive and pharmacoepidemiological studies of patients with COPD have been conducted in CPRD-GOLD, including validation of physicianrecorded COPD diagnosis [Soriano, 2001] and evaluation of COPD co-morbidities [Soriano, 2005]. Studies of pneumonia have also been conducted, including a study of CAP in CPRD-GOLD [Müllerova, 2012] and a validation study of CAP requiring hospitalization in The Health Improvement Network (THIN), which uses the same software as CPRD to capture primary care information [Meropol, 2012].

The database linkages are important to capture hospitalization information and mortality. In CPRD-GOLD, the GP enters information about hospitalizations, including serious pneumonia, from the discharge summary materials sent to their practice. HES includes hospitalization information for the majority of practices in the CPRD-GOLD. These data provide more information about the cause of hospitalization and length of stay than are otherwise available in the primary care record. Finally, we will use the Office of National Statistics linkage to mortality information. Mortality is an important competing risk for any COPD study, as patients are older and have co-morbid diseases due to aging and smoking history.

5.4. Outcome

5.4.1. Feasibility of Pneumonia

Pneumonia is difficult to define in database studies, and preliminary work was performed to better understand the number of pneumonias and coding trends in CPRD-GOLD and HES.

Note that most diagnoses of pneumonia in CPRD-GOLD do not assign an organism or cause based on the summary presented in Table 2.

Table 2Preliminary Count of Community-Acquired Pneumonia Events in
New User Cohort: CPRD-GOLD

		Number of Episodes			odes
			Pne	umonia l	Definitions
		All	Pneumonia	a Other	Tuberculosis
All		583	564	11	8
GPRD Medical	Read Description				
Code (Events)					
572	Pneumonia due to				
	unspecified organism	304	304		
886	Bronchopneumonia due to				
	unspecified organism	90	90		
1849	Lobar (pneumococcal)				
	pneumonia	59	59		
16287	Chest infection - unspecified				
	bronchopneumonia	23	23		•
3683	Basal pneumonia due to				
	unspecified organism	21	21		•
10086	Pneumonia and influenza	15	15		•
9639	Lobar pneumonia due to				
	unspecified organism	12	12		•
25694	Pneumonia due to other				
	specified organisms	9	9		
23095	Bacterial pneumonia NOS	9	9		
5202	Viral pneumonia	8	8		
635	Pulmonary tuberculosis	8			8
4910	Interstitial pneumonia	8		8	
5324	Atypical pneumonia	3	3		
14976	Viral pneumonia NOS	3	3		
28634	Other bacterial pneumonia	3	3		
11440	Pulmonary aspergillus				
	disease	2		2	
26287	Klebsiella				
	pneumoniae/cause/disease				
	classifd/oth chapters	1	1		
30591	Pneumonia due to				
	pseudomonas	1	1		

		Number of Episodes			odes
			Pneu	imonia I	Definitions
		All	Pneumonia	Other	Tuberculosis
34251	Pneumonia due to specified				
	organism NOS	1	1		
12573	Respiratory syncytial virus				
	infection	1		1	
40299	Pneumonia – candidal	1	1		
12423	Pneumonia due to				
	streptococcus	1	1		

Preliminary coding trends were examined in HES and are presented in Table 3. Note that most diagnoses of pneumonia in CPRD do not assign an organism or cause.

Table 3 Preliminary Count of Pneumonia Events in New User Cohort: HES

		No Episodes	Col %
		N	%
All		2,327	100
An ICD10 diagnosis code	ICD10 description		
J18.1	Lobar pneumonia, unspecified	1,292	56
J18.9	Pneumonia, unspecified	782	34
J18.0	Bronchopneumonia, unspecified	124	5
J13	Pneumonia due to Streptococcus pneumoniae	31	1
J15.1	Pneumonia due to Pseudomonas	24	1
J14	Pneumonia due to Haemophilus influenzae	19	1
J15.0	Pneumonia due to Klebsiella pneumoniae	11	0
J15.2	Pneumonia due to staphylococcus	9	0
J17.2	Pneumonia in mycoses	7	0
J16.8	Pneumonia due to other specified infectious		
	organisms	4	0
J18.8	Other pneumonia, organism unspecified	4	0
J10.1	Influenza with oth resp manifest influenza virus identified	4	0
J15.6	Pneumonia due to other aerobic Gram-negative bacteria	3	0
J15.7	Pneumonia due to Mycoplasma pneumoniae	3	0
J17.3	Pneumonia in parasitic diseases	3	0
J15.4	Pneumonia due to other streptococci	2	0
J11.1	Influenza with oth resp manifestation virus not		
	identified	1	0
J11.0	Influenza with pneumonia, virus not identified	1	0
J15.9	Bacterial pneumonia, unspecified	1	0
J15.8	Other bacterial pneumonia	1	0
J15.5	Pneumonia due to Escherichia coli	1	0

Following the preliminary feasibility, subsequent feasibility on the total number of new users was evaluated as described in the protocol and presented in Table 4. This addressed the overlap between CPRD-GOLD and HES and definition of pneumonia episodes. The total number of pneumonia episodes available for the final analysis (e.g., time to first) are described in Table 4, including 283 pneumonia and 106 severe CAP, and 1 HAP. Based on concerns about statistical precision, the protocol analyses were adjusted prior to implementation of analysis.

Pneumonia Events	Year o	f Coho	ort Enti	ry						Total New Users
	2002	2003	2004	2005	2006	2007	2008	2009	2010	
Type of Pneumonia episode										
HAP							1			1
Severe CAP	16	22	13	11	18	7	11	5	3	106
Non-severe CAP	18	23	23	26	23	18	23	17	5	176
All Pneumonia	34	45	36	37	41	25	35	22	8	283

Table 4Count of First Pneumonia Events Including Adjustments for
Episodes: New User Cohort

